15.0.0 Quality Control

All data for the HANDLS study is collected by following detailed Standard Operating Procedures (SOPs) as outlined in the HANDLS Operations Manual. The majority of data is collected electronically, in real time, and is monitored at regular intervals for accuracy and adherence to the protocol by HANDLS computer programmers and information technology specialists. Manually collected data are stored in the research medical record and are reviewed for accuracy and completion daily by the HANDLS Medical Records Specialist. The HANDLS Nurse Practitioner selects medical records at random for monthly audits.

16.0.0 Statistical Considerations

Power analysis. Initial estimates based on the 2000 census data indicate that we needed to visit approximately 35% of the households in each census tract to collect the required 333 individuals. The initial sample of 3,500-4,000 participants is based on power analyses and assumptions about attrition over 20 years. For a power of 80% (the likelihood of finding an effect if it is really present), we can identify moderate effects (magnitude of the differences between groups) for various outcomes with as few as 30 participants per group at the end of the study. Working backwards by assuming 20% attrition after the baseline assessment and 15% attrition between subsequent assessments, we need approximately 3,500-4,000 participants at baseline to yield 1,680 after 20 years.

Data analyses. The study employs standard statistical software depending on the independent and dependent variables being analyzed. Data analyses include parametric and non-parametric statistics for cross-sectional comparisons applying logistic regression and mixed effects modeling as appropriate for the data. Longitudinal analyses will typically require either mixed-effects models, survival analyses, or proportional hazards depending on the data and specific outcome under study.

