HANDLS recruited a fixed cohort as an area probability sample of Baltimore City from August 2004 through November 2009 as Wave 1 (Figure 1). HANDLS Wave 2 entitled *The Association of Personality and Socioeconomic status with Health Status – An Interim Follow-up Study* began in June 2006 under a separate protocol. It was designed as a follow-up telephone interview approximately 18 months after the initial examination (Wave 1) was complete. Wave 2 provided interim contact with study participants, and important interim information regarding their health. Now completed, wave 3 was the first follow-up examination and participants' second visit to our mobile Medical Research Vehicles (MRVs). The current protocol outlines Wave 4, the second follow-up examination and participants' third visit to our mobile Medical Research Vehicles (MRVs). Planned as a follow-up after 3-4 years, Wave 4 consists of health examinations, a telephone dietary-recall interview, renal function assessments, and optional studies of circadian rhythm, structural MRIs, and an evaluation of the subjective experience of diabetes mellitus.

Figure 1. Present and projected HANDLS timeline

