11.0.0 Study Design and Procedures

The HANDLS study is an interdisciplinary, prospective epidemiologic longitudinal study examining the influences and interaction of race and SES on the development of cardiovascular and cerebrovascular health disparities among minority and lower SES subgroups.

HANDLS Wave 4 NIA Protocol 09-AG-N248 — Version 6 – 9/17/2015

The baseline HANDLS sample consists of 3720 community-dwelling African American and white adults aged 30-64. Participants were drawn from 13 neighborhoods (groups of contiguous census tracts) in Baltimore City, sampling representatively across a wide range of socioeconomic and income circumstances. The heuristic study design is a factorial cross of four factors: age, sex, race, and SES with approximately equal numbers of subjects per "cell" (Figure 2). HANDLS is planned as a 20-year longitudinal study of the 3720 individuals accrued (Figure 3). Using our mobile medical research vehicles, we are revisiting each census tract for 2-3 months over the next 3 years.

The 13 neighborhoods identified were selected because they were likely to yield representative distributions of individuals between 30 and 64 years old who are African Americans and whites, men and women, and lower and higher SES.

Study sample. The study recruited an area probability sample of whites and African Americans between 30 and 64 years old from 13 neighborhoods in Baltimore City in both low and high socioeconomic strata as a fixed cohort following the overall design. By collecting a baseline assessment and 5 follow-up triennial assessments over approximately 20 years, there will be sufficient power (>.80) with 30 participants per group (race by SES by sex by age group) remaining after 20 years. There will also be sufficient power (>.80) to compare rates of change among groups after the baseline assessment.

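### Under the plan's own attrition rates and five follow-ups, 1,680 retained needs about 4,000 at baseline; the accrued 3,720 project to about 1,553, or 7.5% short

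*Protocol*

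**What the plan says.** Section 16.0.0 (Power analysis) works backwards from a final group size. It states that moderate effects can be found at 80% power "with as few as 30 participants per group at the end of the study". Then, "assuming 20% attrition after the baseline assessment and 15% attrition between subsequent assessments", it concludes that "we need approximately 3,500-4,000 participants at baseline to yield 1,680 after 20 years".

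Section 11.0.0 (Study sample) supplies the number of assessments: "By collecting a baseline assessment and 5 follow-up triennial assessments over approximately 20 years". It claims power above 0.80 "with 30 participants per group (race by SES by sex by age group) remaining after 20 years".

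The same section gives the cohort obtained: "The baseline HANDLS sample consists of 3720 community-dwelling African American and white adults aged 30-64". Section 4.0.0 repeats 3,720 as the sample size, with an accrual ceiling of 4,000 and accrual in 2004-2009. Section 5.0.0 describes a fixed cohort recruited from August 2004 through November 2009.

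**The concern.** The protocol prints everything needed to check its retention target: two attrition rates, the number of follow-ups, the target and the accrued number. Section 16.0.0 presents the whole span from 3,500 to 4,000 as giving the same final number. A fixed attrition rate cannot do that, because the two ends of the span differ by 500 people at baseline. The calculation was also not redone once accrual closed at 3,720.

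At stake is the statement in section 11.0.0 that 30 people per race-by-SES-by-sex-by-age group will remain and that this gives power above 0.80. If the accrued cohort does not reach the target under the plan's own assumptions, that statement is somewhat too favourable, even before any difference in loss between groups. With recruitment closed, the gap cannot be made up by enrolment.

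**Working it through.** **Inputs**
- Loss of 20% in the first interval and 15% in each later interval (section 16.0.0).
- Five follow-ups, so one 20% interval and four 15% intervals (section 11.0.0).
- Target of 1,680 at the end, with 30 per group (section 16.0.0).
- Planned baseline of 3,500-4,000 (section 16.0.0); accrued baseline of 3,720 (sections 4.0.0 and 11.0.0).

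**Retention**

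Retention = (1 − 0.20) × (1 − 0.15)^4 = 0.80 × 0.5220 = 0.4176.

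**The plan's own figure**

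Baseline needed = 1,680 / 0.4176 = 4,023. From 4,000 the yield is 4,000 × 0.4176 = 1,670, which is 0.6% below 1,680. The stated figure is therefore reproduced, but only at the upper end of the range.

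**Other baselines**

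| Baseline | Expected at fifth follow-up | Against 1,680 |
|---|---|---|
| 3,500 | 1,462 | 13% short |
| 3,720 (accrued) | 1,553 | 7.5% short |
| 4,000 | 1,670 | 0.6% short |

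For 3,720 the gap is 1,680 − 1,553 = 127 people. To come within 3% of the target, the baseline must be at least 0.97 × 1,680 / 0.4176 = 3,902.

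**Per group**

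The number of groups is not printed in the text, and the design figure is not available here. It is inferred as 1,680 / 30 = 56. With equal groups and equal loss, 1,553 / 56 = 27.7 per group, or about 28.

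**Effect on power**

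The protocol states neither alpha nor a test. Assume a two-sided alpha of 0.05 and a comparison of two group means.
- With 30 per group, the standardised difference detectable at 80% power is √(2/30) × (1.960 + 0.842) = 0.72.
- With 27.7 per group, power at that difference is Φ(0.723 × √(27.7/2) − 1.960) = Φ(0.73), about 77%.
- With 27.7 per group, the difference detectable at 80% power is √(2/27.7) × 2.802 = 0.75.

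**The case against.** The strongest reply is that the wording is approximate and that the figure does reproduce at about 4,000. This stands. A reader might infer that 1,680 cannot be obtained at all because 4,023 exceeds both the range and the accrual ceiling of 4,000. The documents do not support that: a difference of 23 people is rounding in a statement that calls itself approximate. The reply does not rescue 3,500 or 3,720.

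A reader might also infer that the schedule contradicts itself, since five triennial visits take one person only to year 15. But entry was staggered from 2004 to 2009, and someone enrolled in late 2009 reaches year 15 in late 2024, the end date in section 4.0.0. Read as the span of the whole study, about 20 years is consistent. A projection with a sixth follow-up therefore has no basis in the text. The position of Wave 4 as the second follow-up examination does not show a shortfall either. Under per-interval attrition, fewer examinations would raise retention: four follow-ups would give 3,720 × 0.80 × 0.85^3 = 1,828. Section 11.0.0, however, fixes five.

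Three further points limit the consequence. Section 16.0.0 explains the size of the initial sample, a decision long made. It names mixed-effects and survival models for longitudinal work, and these use data from people who later leave, so the final head count does not bound every analysis. Section 11.0.0 also makes a separate power claim for rates of change after baseline, which this check does not test. All three stand as limits on severity. They do not remove the mismatch, because section 11.0.0 ties its 20-year claim explicitly to the number remaining and reports 3,720 in the same section.

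**Conclusion.** The point holds in a narrow form. Under the plan's attrition rates and five follow-ups, about 4,000 at baseline are needed to retain 1,680. The lower part of the stated range and the accrued 3,720 do not deliver it. The shortfall for 3,720 is 127 people, and it rests only on figures printed in the protocol.

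The per-group figure of about 28 also needs 56 equal groups and equal loss across them. The fall in power to about 77%, or the rise in detectable difference from 0.72 to 0.75 SD, also needs the assumed alpha and two-group comparison. Unequal loss would leave fewer in the worst-retained groups, but the protocol gives no figures from which to size this.

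Severity is minor to moderate: a planning statement is too favourable by a modest amount, and no Wave 4 procedure or analysis depends on it.

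**What to change.** In section 16.0.0, replace the sentence on the required baseline with wording such as: *3,720 at baseline, five follow-ups, 20% then 15% attrition: about 1,550 expected at the last assessment, about 28 per group.* The number of groups should be stated, so that the per-group figure can be checked.

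In section 11.0.0, restate the claim of 30 per group and power above 0.80 to match. Either give power slightly below 80% at the same effect, or keep 80% and give a slightly larger detectable effect, with the alpha and comparison assumed.

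The number and spacing of follow-ups need no change on this account, and no one further should be enrolled. The cost is protocol wording and one recalculation; the downside is that the stated figures become slightly less favourable.

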17.0.0 Regulatory Requirements

17.1.0 Informed Consent

Wave 4 phase 1& 2. There are three phases to the Wave 4 study. The first phase occurs in the field, at the medical research vehicles (MRVs) or in the participant's home, if they have limited mobility. If the participant has been identified as a home visit participant, consent may be obtained in the home or over the telephone. Among the preparations for their examinations on the medical research vehicles, participants are provided copies of the informed consent documents and are asked to read them. Participants are then instructed to view a consent film about the HANDLS study that explains the purpose of the study and all procedures they have previously reviewed in the informed consent documents. The HANDLS study consenter then reviews each documents with participants a final time, page by page stopping to ask if they have any questions to ensure the participant has a clear understanding of the study, the degree of risk, potential benefits, and alternatives and then provides the participant with an opportunity to ask any further questions and to consider their decision to participate in this next wave of the HANDLS study. If participants agree to take part, signatures will be obtained using an IRB approved hard copy of the informed consent document or electronically using a PC tablet. HANDLS staff provides participants with printed copies for their records and a copy is placed in the research medical record. HANDLS staff sends participants copies of all signed informed consent documents with the results from their examinations.

Alternate home visit consent procedures. This consent will be done as an oral consent, when participants are consented over the telephone. The consent form will be read to the participant verbatim. The participants will have their own copy available to review as the consenter reads it. All elements required by 45 CFR 46.116 are included, as well as required documentation of the oral consenting process using the following:

Is there anything you would like me to repeat? (Responded)	Yes	No
Have you understood everything I have told you? (Responded)	Yes	No
Do you have any questions? (Responded)	Yes	No
Do you agree to participate? (Responded)	Yes	No

Oral documentation

I have read the above informed consent over the phone to (print name of person being consented) ______ and s/he has agreed to answer the questions and participate in this research study.

*Signature recorded on last page

Print name of person reading this consent_____

Print name of witness who observed: _____

Date_____ Time:_____

Wave 4 – optional studies. Informed consent for the Circadian Rhythm Study will take place on the MRVs using in-person procedures. Informed consent for the Neuroimaging Study will take place at the UMD following guidelines set forth by their IRB and Informed consent for the Diabetes study will take place in the community and will follow procedures set forth by the University of Maryland Baltimore County IRB.

Durable Power of Attorney for Health Care Decision Making. During the wave 4 consent process participants will be asked to designate a heath care agent by completing NIH form 200-(10-00) Durable Power of Attorney for Health Care Decision Making. Participants will be informed that the designee will be able to make decisions regarding their participation in HANDLS (and any clinical care related to their participation), in the event they are unable to make their own decisions due to diminished capacity. A copy of the form will be mailed to the person they name and participants will be encouraged to discuss their known desires and values with the designee, their personal physician and their family.

17.2.0 Compensation

The amount of payment to research volunteers is guided by the National Institutes of Health policies. In general, participants are not paid for taking part in research studies at the National Institutes of Health. Reimbursement of travel and subsistence will be offered consistent with NIH guidelines.

Participants may be reimbursed up to a total of \$360.00 for participating in the HANDLS wave 4 study. They may be paid up to \$200 for participating in phase 1 (\$160) and 2 (\$40) of this study. If they participate in phase 3A (Ecological measurement of circadian entrainment pilot study) they will be compensated an additional \$60.00. If they participate in phase 3B (Neuroimaging study) they will be compensated an additional \$50.00. Finally, if a participant decides to enroll in the "Subjective Experience of Diabetes" study they will receive \$50.00.

If a participant is unable to complete all of the tests they may receive a portion of that payment. They will receive payment in the form of an ATM debit card at the end of the each phase. In most cases, the ATM card will be activated by the end of the study visit day. The participant will be instructed to take the card to an ATM machine of their choosing to withdraw payment. Written instructions regarding how to access payments will be provided. Occasionally participants are not able to complete all testing in one visit to the MRVs or some tests require repeating if there are questionable or abnormal results. We would like to be able to offer additional compensation for time and travel to return to the MRVs for return visits. The amount of compensation will vary between \$20.00 and \$80.00 depending on the length of time spent on the MRVs. We anticipate the return visits to be between 1-4 hours. This would include participants who never had a baseline evaluation.

17.3.0 Subject Confidentiality

HANDLS participants' confidentiality will be maintained by informing them of the following:

When results of an NIH research study are reported in medical journals or at scientific meetings, the participants will not be named and/or identified. In most cases, the NIH will not release any information about participant's research involvement without their written permission. However, if they sign a release of information form, for example for an insurance company, the HANDLS Medical Records Specialist will give the insurance company information from the medical records. Participants are informed this information might affect (either favorably or unfavorably) the willingness of the insurance company to sell them insurance.

The participants' are informed that the Privacy Act protects the confidentiality of their medical record. However, the Act allows release of some information from the medical record without permission, for example, if the Food and Drug Administration (FDA), members of Congress, law enforcement officials, or authorized hospital accreditation organizations, require it.

To help us protect privacy, we have obtained a Department of Health and Human Services Certificate of Confidentiality issued by the National Institutes of Health. With this certificate the researchers cannot be forced to disclose information that may identify participants, even by court subpoena, in any federal, state, or local civil, criminal, administrative, legislative or other proceedings. The researchers will use the certificate to resist any demands for information that would identify them, except as explained below. The Certificate cannot be used to resist a demand for information from personnel of the U.S. Department of Health and Human Services that is used for auditing or program evaluation or for information that must be disclosed in order to meet federal regulations. A Certificate of Confidentiality does not prevent participants or a member of their family from voluntarily releasing information about themselves or their involvement in this research. If an insurer, employer, or other person obtains written consent to receive research information, then the researcher may not use the Certificate to withhold that information. The Certificate of Confidentiality does not prevent the researchers from disclosing voluntarily, without participants consent, information that would identify them as a participant in the research project under the following conditions: It does not apply to state requirements to report certain communicable diseases. In addition, the study clinician may be required to report certain cases of abuse, neglect, or suicidal or homicidal intent to the appropriate authorities.

Information regarding who will have access to the data and use of personally identifiable data or private health information (PHI) are described in further detail in sections 14.0.0 (data collection and management procedures) of this protocol.

18.0.0 Participant Safety, Adverse Events, & Problem Reporting

18.1.0 Participant Safety & Intent to Treat

As the HANDLS study cohort has aged (ages 40-74 after 10th year of study), there are many participants who have developed new, more severe, or multiple chronic age-related medical conditions that require treatment. However, in this cohort participants are at times unable to regularly access needed care or are unable to be consistently compliant with medications and therapies. While participants are screened on the telephone and at times in person prior to setting their longitudinal visit appointments, participants usually do not fully relate their current medical status and level of compliance with prescribed medical regimens. Hence, we are at times confronted with participants in need of minor medical intervention. The frequency and severity of presenting symptomatology related to poorly controlled, chronic medical illness varies by participant and neighborhood demographics. Most often they report running low or out of medication because they cannot afford to fill the prescriptions to continue treatment. In those cases, once medically cleared, participants will be given a 2-4 week prescription and/or funds to fill the prescription. Once symptoms are controlled, they will return for their study visit. In these cases, with participants consent, treatment provided will be shared with the primary care physician of record. If the participant does not have a physician and is agreeable, they will be provided the available resources and assistance to obtain a primary care physician and or health insurance, if necessary.

We have determined that at times, it may be necessary to temporarily suspend the research visit for ethical and safety reasons to administer initial urgent care for treatment of significant symptoms and physical examination findings before the participant can be discharged home, to their medical provider or the local emergency department. Circumstances can become quite complicated when participants exercise their right to refuse transport to an emergency department, HANDLS staff may not be able to contact the participant's primary care provider for an urgent appointment or the participant may not have a regular physician. There are five clinical presentations that we anticipate occurring episodically at the time of the HANDLS longitudinal visit and below we outline the proposed participant safety and well-being actions that will occur in keeping with standard medical practice and ethics:

18.1.1 Poorly controlled hypertension and related medical non-compliance

Some participants will have neglected to take their medications on the day of the exam despite being told the night before to take all anti-hypertensive medications and to bring all medications to the visit. This will result in an elevated screening blood pressure reading. Participants with values <200 systolic and <100 diastolic will be asked to take their medica-

tions immediately. Their blood pressure will be monitored for reduction upon which we will allow them to remain for the study visit. If there is no reduction in blood pressure they will be advised to take their mediation as directed and referred to their primary care physician for a blood pressure check for possible modification of their regimen. They will be re-contacted in 30 days to again assess their suitability for reappointment.

Some participants will be newly diagnosed or non-compliant and have no anti-hypertensive medication. These participants will not continue their visit; they will be referred to their primary care physician for evaluation and treatment if they have a primary care physician. If there is no primary care practitioner, we will provide information about appropriate medical clinics in the vicinity in the context of their insurance status and ability to pay. Social work assistance is available on staff to assist medical staff in navigating the financial assessments. If there is no reduction in blood pressure, their visit will be terminated and they will be advised to take their mediation as directed and referred to their primary care physician for a blood pressure check for possible modification of their regimen. They will be re-contacted in 30 days to again assess their suitability for reappointment.

Participants with SBP>200mmHg and/or a DBP >110mmHg will not continue with their visit and will be sent to the closest ER. If they decline, we will document their choice with an Against Medical Advice (AMA) note in the chart signed by the participant. However, in the interest of providing best available care, we will offer the alternate of administering Clon-idine and providing a prescription for standard antihypertensive medications and an appointment for follow-up at the appropriate medical venue. They will be re-contacted in 30 days to again assess their suitability for reappointment.

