18.1.2 Poorly controlled diabetes mellitus and related medical non-compliance

Some participants may present with symptoms of hyperglycemia due to medical or dietary non-compliance. If there are symptoms of hyperglycemia, a finger stick will be done. For participants with elevated glucose levels >400 but < 500 as determined by glucometer monitoring will be asked to take their medications if available. If they have been non-complaint with their medications or have no medications with them, they will be treated with sliding scale regular insulin and referred back to their primary care provider for evaluation after completing their longitudinal visit. If they have no medication at home, in the interest of providing the best care possible, we will provide a prescription for their previously prescribed hypoglycemic agent or an appropriate drug if they are unable to provide the name of the drug previously taken. They will be referred to an appropriate provider for disease management. Participants with glucose >500 will be referred to the ER and their testing suspended. If they refuse ER transport, we will document their choice with an Against Medical Advice (AMA) note in the chart signed by the participant. We will treat with regular insulin and attempt to get the soonest appointment with their provider or a provider at an appropriate medical clinic. These participants will be contacted 30 days after the interrupted testing to assess their suitability for completion of their longitudinal visit.

Some participants may mistakenly take their hypoglycemic agents while they are fasting in preparation for their visit and become hypoglycemic despite being instructed the night

before the visit via telephone to bring their meds to take at the MRV after they have had their blood drawn and are ready for breakfast. Depending on their glucose level using finger stick glucometer monitoring we will administer glucotabs, oral juices or injectable glucagon. Testing will resume when patient is no longer hypoglycemic by finger stick glucometer monitoring.

18.1.3 Poorly controlled asthma/chronic obstructive pulmonary disease (COPD).

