Participants at times are non-compliant with their medications or have run out of their prescriptions and present with or develop symptoms of wheezing or dyspnea. Participants with a pulse oximeter of 85-90% will receive albuterol nebulizer and/or oxygen as directed by the medical staff. If the subject's saturation does not return to 90% or greater after treatment and remains stable, the subject will be referred to the emergency room. Participants with pulse oximeter values <85% will be sent to the local emergency department. They will be recontacted in 30 days to reassess their suitability for reappointment.

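### Section 18.1.1: for participants who skipped their antihypertensive medication, the two blood-pressure tiers do not meet, so a diastolic pressure of 100 to 110 mmHg with systolic up to 200 has no stated action

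*Protocol*

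**What the plan says.** Section 18.1.1 of the protocol has three paragraphs.

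- **Medication skipped that day.** "Participants with values <200 systolic and <100 diastolic will be asked to take their" medication immediately. Pressure is then watched. If it falls, the participant may stay for the visit. If not, the participant is told to take the medication as directed, referred to primary care and re-contacted in 30 days.
- **No medication.** "Some participants will be newly diagnosed or non-compliant and have no anti-hypertensive medication". For this group, "These participants will not continue their visit; they will be referred to their primary care physician for evaluation and treatment", with clinic information given where there is no physician. No blood-pressure limit is stated. Later in the same paragraph comes: "If there is no reduction in blood pressure, their visit will be terminated and they will be advised to take their mediation as directed". Primary-care referral and 30-day re-contact follow.
- **Very high readings.** "Participants with SBP>200mmHg and/or a DBP >110mmHg will not continue with their visit and will be sent to the closest ER". Those who decline sign a note and are offered clonidine, a prescription and a follow-up appointment, with 30-day re-contact.

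The opening of section 18.1.0 adds that participants who are low on or out of medication may, once medically cleared, be given a two- to four-week prescription or funds to fill one. They return for the study visit once symptoms are controlled.

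**The concern.** The first and third paragraphs are meant to work as a lower and an upper tier. Their systolic limits meet at 200, but their diastolic limits are 100 and 110. A participant with medication who reads 180/105 is too high for the lower tier and too low for the upper one.

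This is a decision threshold for participant safety. Within the uncovered band the protocol does not say whether to give the medication and monitor, whether testing may go ahead, or what follow-up applies. The 30-day re-contact in section 18.1.1 is attached to dispositions that this band never receives. The four-day re-contact in the closing rules after section 18.1.5 applies only if the visit is terminated. Read literally, the section gives a milder reading such as 199/99 medication and monitoring, and gives a higher diastolic reading nothing.

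Separately, the no-medication paragraph stops the visit without condition and then makes termination depend on pressure not falling. That is untidy and deserves an editorial note.

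**Working it through.** No sample-size or power figure is involved. The check is whether the two written rules together cover every reading.

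**Inputs (both from section 18.1.1)**

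- Lower tier: SBP < 200 and DBP < 100.
- Emergency-room tier: SBP > 200 or DBP > 110.

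**Step 1: derive the gap.** A reading is uncovered if it fails both rules.

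- Failing the emergency-room rule means SBP ≤ 200 and DBP ≤ 110.
- Failing the lower rule means SBP ≥ 200 or DBP ≥ 100.
- Together: either DBP is 100 to 110 with SBP ≤ 200, or SBP is exactly 200 with DBP < 100.
- Width of the diastolic band: 110 − 100 + 1 = 11 whole-mmHg values.

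**Step 2: enumerate.** The grid is whole-mmHg pairs with SBP 140 to 240 and DBP 80 to 130.

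| Set | Pairs |
|---|---|
| Covered by neither rule | 691 |
| of which DBP 100–110, SBP 140–200 (61 × 11) | 671 |
| of which SBP = 200, DBP 80–99 | 20 |
| Covered by both rules | 0 |

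These counts depend on the grid chosen. They show that the band is solid, not how many participants fall in it.

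**Step 3: worked readings**

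| Reading | Stated action |
|---|---|
| 199/99 | take medication, monitor |
| 150/100 | none |
| 180/105 | none |
| 195/110 | none |
| 150/111 | emergency room |
| 201/95 | emergency room |

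**Step 4: look for a rule elsewhere.** Section 12.0.0 provides for an examination by a physician or nurse practitioner. Section 18.1.0 allows the visit to be suspended for urgent care. The closing rules after section 18.1.5 cover refusal of transport and four-day re-contact. None contains a blood-pressure cut-off. The no-medication paragraph of section 18.1.1 concerns a different group.

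**Step 5: test the repair.** Take one diastolic cut-off c, with lower tier SBP ≤ 200 and DBP ≤ c, and emergency-room tier SBP > 200 or DBP > c. Each rule is then the exact complement of the other. For c = 110 and for c = 100 alike, there are 0 uncovered and 0 doubly covered readings.

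**Step 6: the no-medication paragraph.** The first instruction stops the visit outright, and the later sentence terminates it if pressure has not fallen. No treatment or monitoring that could lower pressure that day is described for this group. Both sentences lead to the same place: visit not continued, primary-care referral, re-contact in 30 days. The later sentence nearly repeats the end of the preceding paragraph and was probably carried over from it.

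**The case against.** The strongest reply is that section 18.1 outlines responses to anticipated presentations and does not replace clinical judgement. Section 18.1.0 ties its actions to standard medical practice and ethics. A clinician examines each participant, and if the visit is stopped the four-day re-contact applies. This stands as a limit on the consequence. It does not remove the gap, because the section chose to give numeric cut-offs and those cut-offs disagree on the diastolic side.

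Three stronger readings are tempting, and the documents do not support them.

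- **That the no-medication paragraph contains a substantive contradiction.** A reader might infer that some of these participants may continue if their pressure falls, or that advising them to take medication makes no sense. The text never says that they may continue, and the unconditional stop comes first. The prescription route in section 18.1.0 means that they may be given medication to take. What remains is a redundant condition.
- **That the neighbouring sections set an exhaustive standard from which blood pressure departs.** Their tiers adjoin only within a chosen range. Section 18.1.2 has "For participants with elevated glucose levels >400 but < 500 as determined by glucometer monitoring" and then "Participants with glucose >500 will be referred to the ER and their testing suspended", which leaves exactly 500 open and states no action for hyperglycaemia at 400 or below. Section 18.1.3 has "Participants with a pulse oximeter of 85-90% will receive albuterol nebulizer and/or oxygen as directed by the medical staff" and sends values below 85% to the emergency department, but states no action above 90%. The gap in section 18.1.1 has to rest on its own two rules, and it does.
- **That participants in the band go without care, or that study results are affected.** Clinicians are present, and nothing in the analysis depends on these thresholds.

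**Conclusion.** The gap holds. For participants who have antihypertensive medication but skipped it, DBP 100 to 110 mmHg with SBP at or below 200 has no stated action. SBP exactly 200 with DBP below 100 is open too, which is trivial. The gap does not extend to participants without medication, whose paragraph has no pressure limits.

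The conclusion assumes only that the two rules are read as written. The protocol does not say whether 100 or 110 was the intended diastolic limit, so that choice belongs to the study clinicians. How many participants present in this band is not stated and cannot be estimated from the document.

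This is a mismatched safety threshold that should be corrected. Its practical effect is limited by clinician oversight. The redundant sentence in the no-medication paragraph is editorial.

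**What to change.** Use one diastolic cut-off in both tiers of section 18.1.1. Either of the following closes the gap:

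1. **Cut-off 110.** Lower tier: SBP ≤ 200 and DBP ≤ 110. Leave the emergency-room rule as it is (SBP > 200 and/or DBP > 110).
2. **Cut-off 100.** Lower tier: SBP ≤ 200 and DBP ≤ 100. Emergency-room rule: SBP > 200 and/or DBP > 100.

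Option 1 brings the 100–110 band under the existing medicate-and-monitor rule. Option 2 sends readings of 101 to 110 to the emergency room, so it would increase referrals by a number the protocol does not allow one to estimate. Neither needs a new pressure target or a new follow-up rule.

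Editorially, in the no-medication paragraph, remove the condition that terminates the visit if pressure has not fallen, since the visit has already been stopped. Keep the primary-care referral, the advice to take as directed any medication prescribed under section 18.1.0, and the 30-day re-contact.

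The cost is a short wording amendment with the documented IRB approval that section 2.0.0 requires. It adds no procedure, visit or data item.
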